5.3 Leukapheresis

Prior to the procedure each patient's venous access will be evaluated. If a patient does not have acceptable venous access a pheresis catheter will need to be inserted into a central vein by qualified personnel and removed directly after leukapheresis. A separate consent form for central venous access will be obtained for such a scenario.

All selected patients will undergo leukapheresis after CRS + HIPEC surgery and screening but before the priming dose of vaccine. The product is delivered immediately to the University of Pittsburgh Cancer Institute Immunotransplantation Center (ITC). The leukapheresis product will be immediately processed as described in the Chemistry, Manufacturing, and Control section of the BB-IND affiliated with this protocol and will be cryopreserved as described.

5.4 Agent Administration

5.4.1 Celecoxib

The drug will be administered orally, at a dose of 200 mg, twice daily on all study treatment days only.

5.4.2 DC vaccine administration

The intranodal and intradermal administration of the DC vaccine will be performed by the investigator/sub-investigator or their designee.

5.4.2.1 *Intra-nodal administration*

The priming dose of vaccine may be administered on any day of the week since it is not followed by the CKM regime. The intranodal injection for the booster doses will be administered on Monday of cycles 1 through 3.

Intranodal administration will consist of ultrasound-guided intranodal injections of the autologous tumor α DC1 vaccine at a target dose of 3×10^6 in 0.5 mL. Due to manufacturing limitations a minimum of 0.5×10^6 cells is acceptable. In order to avoid repetitive scarification of a single lymph node, the patients will have subsequent doses administered at 3 different sites, with the sites rotated as follows: (a) right inguinal lymph nodal group, (b) left inguinal lymph nodal group, (c) right axillary lymph nodal group, and (d) left axillary lymph nodal group. Only one lymph node will be injected at each visit with the dendritic cells. The size of the lymph node to be injected will be a minimum of 5 mm and a maximum size of 20 mm.

5.4.2.2 *Intradermal route*

Intradermal injection will be used to complement the intranodal injections (provide a depot effect) and it can be used as the only route (for all DCs) in case intranodal injection is not feasible. Each portion of the vaccine will be administered using a 1 mL syringe and needle appropriate for intradermal injections and will hold 0.5 mL of the vaccine preparation. The intradermal DC vaccine should be injected in the vicinity of the major nodal basin of the thigh. The nodal basin must not have been previously dissected.

5.4.3 Tumor-selective systemic chemokine modulation regimen (CKM)

The chemokine modulating regimen will be administered over 4 consecutive days (Tuesday to Friday) in the following order:

- Pretreatment: 500 mL Normal saline IV over approximately 60 minutes
- Pre-meds: Acetaminophen (Tylenol) 650 mg x 1 dose; Prochlorperazine (Compazine) 10 mg x 1 dose – administered 30 minutes (± 5 minutes) after starting pre-treatment hydration
- Celecoxib: 200 mg orally, administered any time prior to IFN
- IFN: IV over 20 minutes (± 5 minutes)
- Celecoxib: 200 mg orally followed at least 15 minutes later by rintatolimod
- Rintatolimod: 200 mg (or 100 mg in case of de-escalation) IV, Wednesday and Friday only

of the CKM regimen, initial administration should begin at a slow rate of infusion (approx. 20 cc/hour) and increase to 40cc/hour after approximately 30 minutes. Tubing should be flushed with 30 to 50 mL of normal saline solution upon completion, Administration will be followed by 1 hour of observation and vital signs at 30 (± 5 minutes) and 60 minutes (± 10 minutes)

Pretreatment and pre-meds listed above are recommendations and may be modified based upon institutional SOC requirements and at the discretion of the investigator/sub-investigator.

5.5 Continuation of Booster Vaccines Administration

At the discretion of the treating physician, any patient who completes study treatment or is removed for reasons other than vaccine related AE/SAEs may continue to receive available vaccine. These vaccines may be administered 4-12 weeks apart. Subjects removed will continue to be evaluated for safety, but not be included in the analysis of formal efficacy objectives but may be evaluated in an exploratory manner. These subjects will be evaluated/followed based upon the conventional care evaluations outlined in the study calendar on days of vaccination (i.e., PE, vitals, AE evaluation).

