3.4 Women and pregnancy

Because the effect of the proposed investigational treatment was not studied in pregnant women the potential risks to the fetus cannot be assessed, pregnant females will not be included in the study. However, no female of childbearing potential will be excluded from the study. An effective form of contraception of the woman's choice will be required at all times during study. A pregnancy test will be performed on enrolled women of childbearing potential. Should a woman become pregnant or suspect she is pregnant while participating in this study, she should inform her treating physician immediately.

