5.7 Duration of Study Treatment

In the absence of treatment delays due to adverse event(s), treatment may continue until one of the following criteria applies:

- Disease progression (excluding disease progression during the time between surgery and the CKM regimen, these patients will be allow to continue with study treatment). See also Section 5.5.
- Patient withdraws consent but allows continued follow-up for survival
- Patient non-compliance
- Unacceptable agent specific adverse event(s).
- General or specific changes in the patient's condition render the patient unacceptable for further treatment in the judgment of the investigator/sub-investigator.
- Pregnancy in patient

The reason and date a patient was removed from study treatment must be documented.

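### Section 5.5 does not except pregnancy from continued vaccine, and the calendar schedules no pregnancy test after Week 1

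*Combined protocol and SAP*

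**What the plan says.** Section 5.5 leaves continued vaccination to the treating physician and defines who may have it: "any patient who completes study treatment or is removed for reasons other than vaccine related AE/SAEs may continue to receive available vaccine". Doses may be 4 to 12 weeks apart. The checks attached to them are the "conventional care evaluations outlined in the study calendar on days of vaccination (i.e., PE, vitals, AE evaluation" items.

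Section 5.7 lists six reasons for ending study treatment. One is "Pregnancy in patient". Another is a change in condition that makes the patient "unacceptable for further treatment in the judgment of the investigator/sub-investigator". The pointer "See also Section 5.5" appears only in the disease-progression item.

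Pregnancy and nursing are exclusions in 3.2.2. Section 3.4 explains that pregnant women are left out because the treatment has not been studied in them and fetal risk cannot be judged. It adds that effective contraception "will be required at all times during study", and: "Should a woman become pregnant or suspect she is pregnant while participating in this study, she should inform her treating physician immediately".

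The Section 10 calendar marks a urine pregnancy test at screening and at Week 1 (priming). The columns for the three booster cycles are blank. Footnote 3 limits testing to sexually active women of childbearing potential and asks for a day-1 result before vaccination in cycle 1.

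**The concern.** Section 5.7 closes study treatment to a patient who becomes pregnant, and 5.5 as written lets vaccine resume for her. The reason given in 3.4 for keeping pregnant women out applies equally to a dose given under 5.5.

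The second matter is detection. A rule that stops treatment for pregnancy works only if the pregnancy is known. The priming dose is vaccine alone, whereas each booster adds interferon-alpha, rintatolimod and celecoxib over the following days. The doses with the greater drug exposure are thus the ones without a scheduled test. This gap belongs to the calendar, not to 5.5, but it carries over to 5.5 doses because their listed checks include no pregnancy test.

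**Working it through.** The first part is a comparison of texts; the second is simple arithmetic on the dosing windows.

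**1. Does 5.5 reach a pregnancy stop?**
- The six 5.7 criteria are progression, withdrawn consent, non-compliance, unacceptable agent-specific adverse events, investigator-judged change in condition, and pregnancy.
- Section 5.7 refers to patients who meet these criteria as removed from study treatment, the same verb that 5.5 uses.
- The 5.5 exception matches only one criterion, the adverse-event one, and only where the agent is the vaccine. Pregnancy is outside the exception and so inside the permission.
- Sections 3.2.2 and 3.4 govern screening, inclusion, contraception and reporting. Neither addresses vaccine after removal, and no other section bars it after a pregnancy stop.

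**2. Which doses have a scheduled pregnancy test?**
- Protocol doses in Phase 2: 1 priming + 3 boosters = 4.
- Calendar tests: screening and Week 1. The priming dose is covered, so 4 − 1 = 3 doses have no scheduled test.
- Section 5.2 puts each booster 4 to 12 weeks after the preceding dose. Time since the Week 1 test:
  - booster 1: 4 to 12 weeks
  - booster 2: 2 × 4 to 2 × 12 = 8 to 24 weeks
  - booster 3: 3 × 4 to 3 × 12 = 12 to 36 weeks
- By the calendar's target weeks, booster 3 comes 12 − 1 = 11 weeks after the test.
- The 36 weeks is the end of the window, not a ceiling: 5.2 allows patients who miss a window to receive the remaining courses later.
- For a patient who completes treatment, any 5.5 dose comes after booster 3. No interval is assumed for it.

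**3. Alternative reading of footnote 3.** If cycle 1 there means booster cycle 1, that dose has a test as well. Then 4 − 2 = 2 doses lack one, and booster 3 falls 2 × 4 to 2 × 12 = 8 to 24 weeks after the last test. The gap is smaller but remains.

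**The case against.** The strongest reply is that 5.5 compels nothing. It rests on the treating physician's discretion; 3.4 requires contraception and sends news of a pregnancy to that same physician; and under 5.4.2 "administration of the DC vaccine will be performed by the investigator/sub-investigator or their designee". The cross-reference placed only under progression suggests that 5.5 was written with progression in mind. All of this stands, and it makes vaccination of a woman known to be pregnant unlikely. It does not amount to a written bar, and none of these controls would find a pregnancy that the patient has not recognised.

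Three stronger readings are tempting, and the documents do not support them as errors.
- A reader might infer that 5.5 wrongly reaches every patient stopped for investigator-judged unfitness. Study treatment here is vaccine plus the chemokine-modulating regimen (CKM), and 6.2.2 expressly allows vaccine to go on after CKM is discontinued. A judgment of unfitness may concern CKM only, in which case continued vaccine is consistent with the design. A bar on vaccine after any unfitness judgment would conflict with 6.2.2.
- A reader might infer that Section 3, which allows available vaccine doses after exclusion for any reason, permits vaccine after vaccine toxicity. That text is a general replacement rule. The specific rules in 5.5 and 6.2.1 address vaccine toxicity and would ordinarily govern.
- A reader might infer that 6.2.2 restarts CKM at a 33% reduction after a life-threatening reaction that 6.4 says should end protocol therapy. Section 6.4 is the specific rule for hypersensitivity to interferon-alpha or rintatolimod, whereas 6.2.2 is the general rule by grade.

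**Conclusion.** The point holds in two parts. First, the 5.5 exception omits pregnancy, so the written permission reopens vaccine to a patient whom 5.7 has stopped and whom 3.2.2 and 3.4 would not have admitted. Second, and separately, three of the four protocol doses and every 5.5 dose have no scheduled pregnancy test; the count is two of four if footnote 3 refers to booster cycle 1.

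This is a minor patient-safety improvement. A reader might infer that the protocol intends or expects pregnant patients to be vaccinated; the documents do not support that, since 5.5 is permissive and its wider reach looks unintended. The documents give no pregnancy rate or number of 5.5 doses, so no count of affected patients can be given. No efficacy figure changes: 5.5 already keeps removed patients out of the formal efficacy analysis. The week ranges assume dosing within the 5.2 windows.

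**What to change.** - **Section 5.5:** extend the exception to three reasons: a vaccine-related AE or SAE, pregnancy, or an investigator judgment under 5.7 that the patient is unacceptable for further vaccine. Say that a judgment limited to CKM does not bar vaccine, in line with 6.2.2.
- **Section 10 calendar and 5.5:** require a urine pregnancy test in women of childbearing potential before each booster and each 5.5 dose, and make clear in footnote 3 which cycle is meant.
- **Optional clarifications, not corrections of error:** make the Section 3 allowance for available doses subject to 5.5, and state in 6.2.2 that 6.4 governs severe hypersensitivity to interferon-alpha or rintatolimod.

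The cost is small. A woman of childbearing potential who receives all three boosters has three more urine tests (two on the alternative reading of footnote 3), plus one for each 5.5 dose. The treating physician loses a little discretion. A patient who recovers after being judged unfit for vaccine would need the investigator to revise that judgment before receiving more.

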5.6 Safety evaluation and monitoring

The recommended starting dose of the combination of vaccine and chemokine modulation will be determined in the Phase 1 portion of the trial. In order to refine the estimate of the RLT rate during the efficacy phase we will apply continual Bayesian monitoring of treatment-related regimen limiting toxicities and, if needed, impose a stopping rule that permits suspension of the trial by the investigator for review by the Data Safety and Monitoring Committee (DSMC). Details and a monitoring table are in section 13.

5.7 Duration of Study Treatment

In the absence of treatment delays due to adverse event(s), treatment may continue until one of the following criteria applies:

- Disease progression (excluding disease progression during the time between surgery and the CKM regimen, these patients will be allow to continue with study treatment). See also Section 5.5.
- Patient withdraws consent but allows continued follow-up for survival
- Patient non-compliance
- Unacceptable agent specific adverse event(s).
- General or specific changes in the patient's condition render the patient unacceptable for further treatment in the judgment of the investigator/sub-investigator.
- Pregnancy in patient

The reason and date a patient was removed from study treatment must be documented.

5.8 Off Study Treatment Visit

Within 1-2 weeks after the last day of study treatment, patients will have their last study specific clinical visit. At the discretion of the treating physician, the tests/procedures due to be performed at the Off Study Treatment visit may be performed on the last day of the CKM treatment for scheduling purposes.

AEs and conmeds will be collected for up to 5 days post last dose of treatment. Any patient experiencing study related SAE will be followed until resolution to Grade 1 or baseline.

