- Greater than or equal to grade 3 non-hematologic adverse events, except for the following grade 3 toxicities unless they last greater than one week:
 - Flu-like symptoms/constitutional symptoms (i.e., fever, chills, arthralgias, myalgias)
 - Depression, anxiety, restlessness, or insomnia
 - Manageable GI symptoms (i.e., nausea, diarrhea)

The observation period for each patient in the Phase 1 portion of this study will be up to 5 weeks (i.e. up to and including the Friday 1 week after the end of the chemokine modulating regimen).

Note: The last 2 patients in the Phase 1 cohort that determines the RP2D will continue on to the Phase 2 part of the trial and will receive the 2nd and 3rd booster/CKM cycles and follow-up per the Phase 2 portion of this protocol. All patients in the dose finding cohort will be followed for primary efficacy endpoints as well as have blood and serum drawn for corollary studies.

Patients in the Phase 1 (safety) cohort will receive their study treatment and will be monitored for RLTs according to the following timeline:

Eligibility	ECOG performance status, blood work CRS + HIPEC
Screening	History and physical exam, ECOG performance status, blood work, and evaluation of tumor material
Post-surgery (after the discharge from the hospital)	Leukapheresis
Week 1* (upon recovery from surgery; at least 4 weeks after surgery)	Priming Vaccine dose; no chemokine modulation Monday: α DC1 vaccine Oral celecoxib, 200 mg, twice daily on the day of vaccination Tues – Sun: oral celecoxib 200mg, once daily
Weeks 2-3	Rest – continue oral celecoxib, 200 mg, once daily
Week 4	Cycle 1 (“booster cycle”) Monday: α DC1 vaccine Tues – Fri: Systemic Chemokine Modulation Regimen. Oral celecoxib, 200 mg, twice daily on the days of vaccination and CKM. Celecoxib will be discontinued after CKM on Friday. Rintatolimod is only administered on Wednesday and Friday.
Off study treatment	Follow-up for Time-to-Progression/occurrence (TTP)

CRS: Cytoreductive surgery; HIPEC: Hyperthermic intraperitoneal chemoperfusion; TTP: Time-to-progression

*Adjuvant immunotherapy may be delayed until full recovery at the discretion of the investigator/sub-investigator. The beginning of immunotherapy will be considered week 1 of the experimental treatment and the timing of all subsequent elements of treatment will be based upon the first vaccine.

5.2 Phase 2: Efficacy assessment of α DC1 vaccine followed by the chemokine-modulatory regimen (CKM)

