7. ADVERSE EVENTS: LIST AND REPORTING REQUIREMENTS

Adverse event (AE) monitoring and reporting is a routine part of every clinical trial. The following list of AEs (Section 7.1) and the characteristics of an observed AE (Section 7.2) will determine whether the event requires expedited reporting **in addition** to routine reporting.

Note that Phase 2 of this study will include two periods of immunotherapy, administered before and after adjuvant chemotherapy (minimum 5 day wash-out periods), in order to separate potential toxicities of the chemokine modulatory regimen (all three factors are short-acting), from the anticipated toxicities of adjuvant chemotherapy. For this reason, we will only collect the toxicity data from the periods of immunotherapy. All toxicities related to the vaccine or CKM must be followed until resolution to grade 1 or baseline.

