7.1 Adverse Events and Risks List(s)

7.1.1 DC Vaccine

Dendritic cell vaccines have been investigated extensively in a number of centers and to date, have not been reported to be associated with limiting toxicities or adverse side effects. DC vaccines carry a potential risk of development of autoimmune disease (such as lupus, or vitiligo). Whereas development of vitiligo has been reported with similar vaccines administered to melanoma patients (and correlated with positive response to vaccination), other side effects have not been reported. Although, based on previous trials with DC-based vaccines, the possibility of developing an allergic reaction to DC-based vaccines is rare there is a chance that patients could have an allergic reaction to the vaccine.

While other classes of immunotherapeutic drugs, particularly the currently approved immune checkpoint blocker, Yervoy [Ipilimumab] can produce significant toxicity, such as enterocolitis, hepatitis, dermatitis (including toxic epidermal necrolysis), neuropathy, and endocrinopathy, due to its ability to promote polyclonal T-cell activation and proliferation, such effects have not been described following application of DC cancer vaccines, including previously-administered alpha-DC1-based vaccines, their combinations with a long acting TLR3 ligand poly-ICLC (Okada,

Kalinski, Bartlett, J. Clin. Onc. 29 (3):330-336, 2011) or their combinations with the proposed CKM regimen in our patients treated on compassionate-use protocols.

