7.3 Recording/Reporting requirements

7.3.1 Eliciting AE Information

Research subjects will be routinely questioned about AEs at study visits.

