6. Peripheral blood for potential correlative studies will be collected at the following time points: once during the pre-screening, within 60 minutes before the vaccinations of the priming cycle, and booster cycles 1 and 2; and within 60 minutes after completing booster cycle 2 on Friday. Peripheral blood for potential correlative studies may additionally be drawn within 60 minutes before the vaccination of booster cycle 3 on Monday and within 60 minutes after completing booster cycles 1 and 3 on Friday.
7. Performed within 2 weeks prior to the priming dose of vaccine and 5 business days prior to cycles 1, 2 and 3 vaccines.
8. CT or MRI imaging should be performed prior to cycle 1 if the recovery period from surgery is greater than 6 weeks.
9. At the discretion of the treating physician, the tests/procedures due to be performed at the Off Study Treatment visit may be performed on the last day of the CKM treatment for scheduling purposes.
10. Performed as routine pre-operative evaluation.
11. AEs /conmeds should be collected up to 5 days after treatment, unless considered clinically significant or serious in nature in which case they will be followed until resolution or Grade 1.

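### Phase 1 observes for regimen-limiting toxicity to day 7 after CKM, but adverse-event collection stops at day 5, so late-onset events may be missed

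*Combined protocol and SAP*

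**What the plan says.** **RLT window.** Section 5.1 sets the Phase 1 observation period as "up to and including the Friday 1 week after the end of the chemokine modulating regimen". The same section makes one week of observation after CKM a condition for starting CKM in the next patient or at the next dose.

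**Duration criterion.** Non-haematologic events of grade 3 or higher related to CKM are RLTs, "except for the following grade 3 toxicities unless they last greater than one week". The listed exceptions are constitutional, psychiatric and manageable gastrointestinal symptoms.

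**Collection.** Section 5.8 says "AEs and conmeds will be collected for up to 5 days post last dose of treatment". Footnote 11 of the study calendar says "AEs /conmeds should be collected up to 5 days after treatment", but exempts clinically significant or serious events, which are followed until they settle.

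**Contact.** Section 7.3.1 says "Research subjects will be routinely questioned about AEs at study visits". The off-treatment visit falls one to two weeks after the last treatment day, and the calendar marks adverse events there. At the treating physician's discretion, its tests and procedures "may be performed on the last day of the CKM treatment for scheduling purposes". The Phase 1 timeline in 5.1 lists no contact in the observation week.

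**Follow-up of known events.** Sections 7 and 7.3.2 follow related or associated events until they settle, with no day limit. Section 6.1 does the same for a declared Phase 1 RLT.

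**The concern.** The RLT is the event from which Phase 1 defines the recommended Phase 2 dose (RP2D), and that dose is the Phase 1 primary endpoint. The observation period and the collection rule for the same patients end on different days, and collection ends first. Phase 1 has a single booster cycle. For every patient who does not continue into Phase 2, the last dose in 5.8 is therefore the dose whose RLT window is being read.

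An RLT that goes unrecorded can only make a tier look safer than it is. With two patients per tier before escalation, single events decide the next assignment.

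**Working it through.** **1. The plan's own figure.** The suspension table in 13.4 uses a Beta(1.93, 4.74) prior and suspends when the posterior probability of an RLT rate above 0.30 exceeds 0.80. For 5 RLTs in 10 patients the posterior is Beta(1.93 + 5, 4.74 + 5). That gives P(rate > 0.30) = 0.831 and a binomial tail of 0.15, both as printed. All 22 rows reproduce. Any problem lies in the count fed to the rules, not in this table.

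**2. Day count.** Let day 0 be the last CKM Friday.
- Collection (5.8, footnote 11) ends on day 0 + 5 = day 5, the Wednesday.
- RLT observation (5.1) ends on day 0 + 7 = day 7, the next Friday.
- Days in the window but outside routine collection: 7 − 5 = 2, namely days 6 and 7.

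**3. Duration criterion.** An event with onset on day s exceeds one week only after day s + 7.

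| Onset | Exceeds one week after |
|---|---|
| Day −3 (Tuesday, first CKM day) | day 4 |
| Day 0 (last CKM day) | day 7 |
| Day 5 (last collection day) | day 12 |

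An onset on day 0 or later cannot qualify by day 7. If it is related and recorded by day 5, sections 7 and 7.3.2 keep it under follow-up, so its duration becomes known eventually. What is missing is its status in the meantime. Section 5.1 also mentions a two-week difference between consecutive patients. If that is read as Tuesday to Tuesday, the next CKM starts on day −3 + 14 = day 11. Onsets with s + 7 ≥ 11, that is days 4 to 7, are still undecided then. A pending category exists on either reading.

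The leukopenia/neutropenia criterion (at least 96 hours) fits inside five days, so the mismatch in days does not touch it.

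**4. Effect on the escalation rule.** After two patients on a tier:
- 0 RLTs: proportion 0/2 = 0, not above 0.30, so the next higher dose.
- 1 RLT: proportion 1/2 = 0.50, above 0.30, so the next lower dose.

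One missed event can reverse the direction. Likewise, 0 RLTs in 2 + 2 + 6 = 10 patients makes tier 3 the RP2D, whereas a single RLT starts the up-and-down design, which runs to 15 patients.

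**5. Sensitivity (assumed).** The documents do not give the share m of RLTs that would be missed. I assume 0 to 30% to show the range. The probability of no recorded RLT among the six tier-3 patients is (1 − p(1 − m))^6, where p is the true rate.

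| True rate p | m = 0 | 10% | 20% | 30% |
|---|---|---|---|---|
| 0.30 | 0.118 | 0.151 | 0.193 | 0.243 |
| 0.40 | 0.047 | 0.069 | 0.099 | 0.139 |

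The 13.4 rule is also sensitive to its input. With looks at the 22 tabulated sample sizes and a true rate of 0.40, the probability of ever suspending is 0.988, 0.905, 0.659 and 0.345 for the same values of m. This does not show that Phase 2 loses events. It shows why the window behind that count should be stated.

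**The case against.** The best defence is that a specific Phase 1 duty to observe for one week can stand beside a general five-day rule. Section 7.3.2 records every observed or volunteered event without a day limit, and the off-treatment visit, where events are marked, falls by default on day 7 or later. The calendar note moves tests and procedures; it does not say that the visit is cancelled or the observation week waived. Section 7 also describes the CKM agents as short-acting. These points make it likely that many late events would surface. They do not remove the conflict: 5.8 states a shorter limit for the same patients, the follow-up rules act on events already known, and no contact at the end of the window is required once the procedures have been moved.

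Four stronger readings are tempting, and the documents do not support them.
- *RLTs that need more than a week cannot be ascertained.* Sections 7 and 7.3.2 and the exemption in footnote 11 follow related or clinically significant events until they settle. Only the interim classification is open.
- *Two of seven days means 29% of RLTs are lost.* A share of days is not a share of events. Over the whole observation period, priming Monday to Friday of week 5 (4 × 7 + 5 = 33 days), the same gap is 2/33, or 6%.
- *The Phase 2 RLT window is five days.* The one-week window is stated for Phase 1 only, and no Phase 2 window is given. Section 7 says "we will only collect the toxicity data from the periods of immunotherapy", with the stated aim of separating CKM toxicity from chemotherapy toxicity, and events are marked at each later cycle visit.
- *The mismatch explains why autoimmune disease, named as a risk in 7.1.1, could be missed.* Late autoimmunity would fall outside a seven-day window too, so aligning the windows would not address it.

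**Conclusion.** The point holds for Phase 1. Sections 5.1 and 5.8 with footnote 11 contradict each other by two days for new-onset events, with no guaranteed contact in the observation week. In addition, the plan does not say how a listed grade 3 event of undecided duration counts when the observation week closes.

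RLTs may therefore be under-counted, and any loss runs one way, toward escalation. The size cannot be derived, because the frequency of late-onset events is not given; the sensitivity figures rest on an assumed missed share. The day count takes the last CKM Friday as the last dose. That fits Phase 1 patients who stop after one booster cycle, but not those who continue into Phase 2. For Phase 2 the finding is only that 13.4 states no RLT window.

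**What to change.** Reconcile the sections as follows.
- In 5.8 and footnote 11, run Phase 1 adverse-event collection at least to the end of the RLT observation period in 5.1.
- In 5.8 and footnote 9, state that moving the off-treatment procedures does not replace an RLT check at the end of that period; a telephone contact is enough.
- In 5.1, state how a listed grade 3 event whose duration is still pending is classified for the escalation decision. The choice belongs to the sponsor.
- In 13.4, state the RLT ascertainment window used for the Phase 2 count and how it relates to the Phase 1 window.

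The cost is two more days of recording per Phase 1 patient, one telephone call where the procedures were moved, and wording changes. Where chemotherapy starts about day 5, events on days 6 and 7 will need an attribution judgement. The 13.4 table does not change.
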